9.2.2.1.4. ALSAQ-40 - Changes from Baseline

The secondary endpoint of ALSAQ-40 change from baseline visit throughout the periods of both MT-1186-A02 and MT-1186-A04 will be analyzed using the FAS and will use the same methodology as described for the ALSFRS-R analysis replacing the ALSFRS-R at baseline covariate with ALSAQ-40 at baseline. The LSMEANS estimates for the mean change from baseline to Week 24 (A02), Week 48 (A02), Week 72 (A04 Week 24)) and Week 96 (A04 Week 48) as well as the difference of the estimates between oral edaravone 105 mg daily versus oral edaravone 105 mg on/off regimen will be displayed with their corresponding standard errors, p-values, and 95% confidence interval.

9.2.2.1.5. Time to death or permanent assisted mechanical ventilation (≥23 hours/day):

The same methodologies as specified for the primary analysis and supportive analysis for the

Mitsubishi Tanabe Pharma America, Inc.

primary endpoint will be performed for this endpoint using all randomized analysis set.

9.2.2.1.6. Time to death

The same methodologies as specified for the primary analysis and supportive analysis for the primary endpoint will be performed for this endpoint, using all randomized analysis set.

9.2.2.2. Exploratory Endpoints

The following exploratory endpoints will be analyzed without overall Type I error correction. All available data regardless of use of additional/new AMX0035 treatment (ICE1) drug will be included.

9.2.2.2.1. %Slow Vital Capacity (%SVC) - Changes from Baseline

The exploratory endpoint of %SVC change from baseline throughout the periods of both MT-1186-A02 and MT-1186-A04 will be performed using the FAS and will use the same methodology as described for the ALSFRS-R analysis replacing the ALSFRS-R at baseline covariate with %SVC at baseline. The LSMEANS estimates for the mean change from baseline to Week 4 (A02), Week 8 (A02), Week 12 (A02), Week 24 (A02), Week 36 (A02), Week 48 (A02 and A04 Day 1), Week 72 (A04 Week 24) and Week 96 (A04 Week 48) as well as the difference of the estimates between oral edaravone 105 mg daily versus oral edaravone 105 mg on/off regimen will be displayed with their corresponding standard errors, p-values, and 95% confidence interval.

9.2.2.2. Body Weight - Change from Baseline

The exploratory endpoint of changes from baseline in Body Weight throughout the periods of both MT-1186-A02 and MT-1186-A04 will be analyzed using the FAS and will use the same methodology as specified for the ALSFRS-R analysis replacing the ALSFRS-R at baseline covariate with Body Weight at baseline. The LSMEANS estimates for the mean change from baseline to Week 4 (A02), Week 8 (A02), Week 12 (A02), Week 24 (A02), Week 36 (A02), Week 48 (A02 and A04 Day 1), Week 60 (A04 Week 12), Week 72 (A04 Week 24), Week 84 (A04 Week 36) and Week 96 (A04 Week 48), as well as the difference of the estimates between oral edaravone 105 mg daily versus oral edaravone 105 mg on/off regimen will be displayed with their corresponding standard errors, p-values, and 95% confidence interval.

9.2.2.2.3. King's ALS Clinical Stage Derived from ALSFRS-R Score and Death Event

King's ALS Clinical Stage analysis will be done using the FAS. A shift table to each visit throughout the periods of both MT-1186-A02 and MT-1186-A04 from baseline category will be summarized using number and percentages.

Mitsubishi Tanabe Pharma America, Inc.

For the Kings ALS Clinical Staging System, attention will focus on two events of clinical progression:

- Any decline in stage from baseline
- Any \geq 2-stage decline from baseline

These events will be analyzed in terms of both the proportion of patients who will experience the events between baseline and visit Week 96 (A04 Week 48) in MT-1186-A04 using chi square test for proportions, as well as the time to these events using stratified log rank test using the randomization strata of ALSFRS-R rate of decline score during the screening period (2 levels strata of -1,-2 or -3,-4), Geographical Region (3 levels strata of Europe, America or Asia Pacific). For the latter, study dropouts prior to any event will be treated as censored as of the date of their first missing assessment. The time to event will be also displayed using the Kaplan Meier figure. Comparisons will be made between treatment groups on an overall basis, as well as controlling for King's stage at baseline using Cochran–Mantel–Haenszel test (CMH).

Mitsubishi Tanabe Pharma America, Inc.

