8.3.2.3. King's ALS Clinical Stage Derived from ALSFRS-R Score and Death Event

The King's ALS Clinical Staging System describes functional progression of ALS in terms of magnitude of disease involvement of different CNS regions (bulbar, upper limb, lower limb, need for gastrostomy and need for tracheostomy); according to its developers, the system was designed to inform patient-care decision making, resource allocation, research classifications, and clinical trial design¹¹. Stages 1, 2, and 3 refer to the number of CNS regions (bulbar, upper limb, lower limb) involved at assessment, as described in *Table 4* below. Stage 4A is defined solely by impairment of swallowing sufficient to require gastrostomy, and Stage 4B is defined solely by respiratory involvement sufficient to require ventilatory support. Functional involvement of three CNS regions is not a prerequisite to Stage 4A or 4B.

While the King's ALS Clinical Staging System was designed initially for use as an assessment tool to be used in clinic, Balendra and colleagues 12 developed a method for estimating King's ALS Clinical Stages based on responses to ALSFRS-R items Q1 (speech), Q2 (salivation), Q3 (swallowing), Q4 (handwriting), Q5A/Q5B (self-feeding), Q8 (walking), Q10 (dyspnea), and Q12 (respiratory insufficiency) 12. The algorithm for mapping from responses to these items to King's Stage is also described in *Table 4*.

Table 4: King's ALS Clinical Staging System

King's Stage	Definition	Item Mapping
1	Functional involvement of 1 CNS region	Bulbar involvement Score ≤3 on Q1, Q2, or Q3
2	Functional involvement of 2 CNS regions	Upper limb involvement Score ≤3 on Q4 or Q5A
3	Functional involvement of 3 CNS regions	Lower limb involvement Score ≤3 on Q8
4A	Need for gastrostomy	If Q5B is answered, rather than Q5A
4B	Need for non-invasive ventilation	Score of 0 on Q10 or score ≤3 on Q12
_5	Death	

CNS: Central nervous system regions are bulbar, upper limb, and lower limb

Mitsubishi Tanabe Pharma America, Inc.

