Since the MT-1186-A02 and MT-1186-A04 clinical trials will not collect information on King's Stage directly, ALSFRS-R item responses and patients' survival will be mapped to stages for every ALSFRS-R collected visit using the above published algorithm and patientlevel data. Patients with baseline ALSFRS-R assessments at MT-1186-A02 that will not meet criteria for lower limb, upper limb, or bulbar involvement, and that also will not have evidence of Stage 4A or Stage 4B, will be designated "Stage 0", as their assessments could not be mapped to the King's ALS Clinical Staging System. For the King's stage derivation, the available ALSFRS-R data at each analysis visit will be used in the subjects who were not dead. If the subject was reported as death from the last observation visit to last day of the nearest analysis visit window, the King's stage from the analysis visit will be Stage 5. If a subject not reported as death will have missing ALSFRS-R assessment at each visit, the last observation will be carried forward for the last King's stage value: In the vast majority of circumstances patients will either remain in the same clinical stage from one assessment to the next or they will experience a decline in stage. In those relatively rare instances, in which subject will be found to improve from one assessment to the next, the value from their immediately prior assessment will be used rather than the actual observed value, because the improvement will be considered to be temporary or spurious.

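### In the King's staging analysis, a subject at Stage 4B at baseline cannot meet the two-stage decline event, even by dying

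*SAP*

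**What the plan says.** SAP 9.2.2.2.3 plans shift tables of King's stage and then says that "attention will focus on two events of clinical progression". The first is "Any decline in stage from baseline". The second is a decline of two or more stages ("2-stage decline from baseline"). Each event is compared between arms as a proportion by chi-square, as a time to event by stratified log-rank test, and again controlling for baseline King's stage by a Cochran-Mantel-Haenszel (CMH) test. The analysis set is the FAS.

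SAP 8.3.2.3 and its Table 4 list the stages as 1, 2, 3, 4A, 4B and 5, where 5 is death. For a subject who dies, "the King's stage from the analysis visit will be Stage 5". Stage 0 is added for subjects who cannot be mapped at baseline and "that also will not have evidence of Stage 4A or Stage 4B, will be designated" as such, so the SAP allows for subjects at 4A or 4B at baseline. Stage 4 does not require advanced multi-region disease: "Functional involvement of three CNS regions is not a prerequisite to Stage 4A or 4B". Also, "Stage 4B is defined solely by respiratory involvement sufficient to require ventilatory support", which Table 4 implements as a score of 0 on ALSFRS-R item 10 or of 3 or less on item 12. In Protocol Appendix 2, a 3 on item 12 means intermittent BiPAP use.

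The only censoring rule in SAP 9.2.2.2.3 is that "study dropouts prior to any event will be treated as censored".

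**The concern.** A fixed step count on a bounded scale leaves subjects near the top with no room to have the event. Here the top of the scale is death. A subject who starts at 4B and dies has had the worst possible outcome and is recorded as not having had the larger of the two progression events.

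This is out of line with the rest of the plan. The primary endpoint makes death an event by composite strategy (SAP 3.2.1), CAFS ranks every death below every survivor (SAP 8.3.2.2), and the King's endpoint itself is described as derived from ALSFRS-R score and death (SAP 3.3.3). At stake is how one exploratory event is interpreted: its overall proportion and its log-rank comparison include subjects who cannot have the event, and deaths among them do not register.

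**Working it through.** The plan states no figure for this endpoint, so there is none to reproduce. The check is a count of steps.

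**Step 1: steps from each baseline stage to death.** The stage order comes from SAP 8.3.2.3. Because the SAP does not say how 4A and 4B count, both codings are shown.

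| Baseline stage | Steps to death, 4A and 4B one level | Steps to death, 4A and 4B separate |
|---|---|---|
| 0 | 5 | 6 |
| 1 | 4 | 5 |
| 2 | 3 | 4 |
| 3 | 2 | 3 |
| 4A | 1 | 2 |
| 4B | 1 | 1 |

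The second event needs at least 2 steps. Death from 4B fails under both codings; death from 4A fails only under the first. Every death meets the first event, which needs 1 step.

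**Step 2: is there another route to the event from 4B?** No. The only stage beyond 4B is death, and SAP 8.3.2.3 replaces any observed improvement with the preceding value.

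**Step 3: does any rule rescue the case?** Neither SAP 8.3.2.3 nor 9.2.2.2.3 counts death as the second event regardless of baseline stage, or removes Stage 4 subjects from that analysis. The censoring rule is about dropouts and does not say what happens to a death that is not an event.

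**Step 4: effect on each test of the second event.**
- Chi-square: the subject is in the denominator and never in the numerator. If a fraction f of each arm cannot have the event, the observed proportion is (1 − f) times the proportion among those who can, and the difference between arms shrinks by the same factor. With f assumed to be 0.05 or 0.10, the factor is 0.95 or 0.90.
- Log-rank: the subject is at risk until censored and cannot contribute an event.
- CMH: a baseline stratum with no events adds zero to the numerator and zero to the variance. It neither dilutes nor informs the test.

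**Step 5: possible number of deaths.** Affected deaths = N × (share at 4B at baseline) × (share of these who die). N = 384 randomized (SAP 4.2), an upper limit for the FAS. Both shares are assumptions, because the documents give neither.
- 0% at 4B: 0
- 1% at 4B, 20% to 60% dying: 384 × 0.01 × 0.20 = 0.8 to 384 × 0.01 × 0.60 = 2.3
- 5% at 4B: 384 × 0.05 × 0.20 = 3.8 to 384 × 0.05 × 0.60 = 11.5
- 10% at 4B: 384 × 0.10 × 0.20 = 7.7 to 384 × 0.10 × 0.60 = 23.0

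The upper values are generous. SAP 4.2 reports that 202 of the 384 entered MT-1186-A04, SAP 5.1 limits the analysis to data accumulated up to the cessation of MT-1186-A02, and SAP 5.2 says no final analysis will be done.

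**The case against.** The best defence is that a two-stage threshold measures size of change. Failing it means not having declined two stages, which is not the same as not having progressed. The companion event counts every death from every baseline stage, the shift tables show moves from 4B to 5, and death also enters the primary endpoint, CAFS and time to death. All of that stands. A reader might infer that the King's analysis as a whole treats some deaths as non-progression or loses them; the documents do not support this. The gap is confined to one of the two events.

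A reader might also infer that the CMH comparison is damaged. It is not. An event-free stratum drops out, so controlling for baseline stage protects that comparison from dilution, although it does not bring the missed deaths in.

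Nor does the dropout rule show that these deaths are censored as dropouts. It is silent on them.

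Finally, counting a one-step change as an event alters what the event means, the protocol planned only shift tables for this endpoint (Protocol 17.4.5.6), and SAP 9.2.2.2 applies no type I error correction. These are fair points, and they limit the importance of the concern. They do not change the result for a subject who starts at 4B and dies.

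**Conclusion.** The point holds as a matter of definition. As written, the two-stage event cannot be met from 4B at baseline under any coding, nor from 4A if 4A and 4B are one level. A death in such a subject is a non-event in the overall chi-square test and cannot be an event in the log-rank test.

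Its size is unknown. It is tempting to put a firm number on the deaths missed, but the documents contain neither the baseline stage distribution nor the MT-1186-A02 entry criteria. They allow for 4A or 4B at baseline without showing that anyone was there, and zero is possible. The figures in the working illustrate assumed shares only.

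The unstated step coding has a second consequence that involves no deaths: a move from Stage 3 to 4B is two steps if 4A and 4B are separate and one step if they are not.

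This is a small, worthwhile improvement to an exploratory endpoint and affects no primary or secondary conclusion.

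**What to change.** In SAP 9.2.2.2.3, define the second event as a decline of at least two stages from baseline or death, with the date of death as the event date when death is what meets it. Death then counts from any baseline stage. Excluding subjects who cannot decline two stages would be weaker, because it would leave their deaths out of this event.

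In SAP 8.3.2.3, add one sentence saying whether 4A and 4B are one level or two ordered steps. Merging them is not required. Once death counts from any stage, the problem is solved under either coding, and merging would stop a move from 4A to 4B counting as a decline.

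The cost is two sentences and a small programming change. Dates of death are already collected (Protocol 12.2.2; SAP 8.3.2.2.3). The downside is that the event becomes a composite and no longer a pure two-step change, so its label in the tables should say so. The change should be settled before the King's data are analysed by treatment arm; if that has already happened, report the revised event beside the planned one and mark it as added.

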4.2. Sample Size and Power Considerations

In total, approximately 300 subjects who have successfully completed Study MT-1186-A02 are anticipated to be enrolled in this MT-1186-A04 study. A formal sample size calculation was not performed. However, data from 380 subjects (190 subjects per group) randomized in Study MT-1186-A02 will be included for all analyses. Hence, using MT-1186-A02 and MT-1186-A04 survival data and assuming 65% survival rate of the primary endpoint for the control group, the planned sample size of 190 subjects per group initially randomized in Study MT-1186-A02 will provide 70% power to detect a statistically significant result if the true hazard ratio between edaravone 105 mg daily (test) and edaravone 105 mg on/off regimen (control) in the primary endpoint is HR=0.775 (implying 22.5% risk reduction in the hazard due to daily treatment). This calculation of 70% power assumes a 2-sided alpha of 20% based on a rare disease condition (Hilgers RD et al., 201614) using the log-rank test and a follow-up time of up to 48 weeks in Study MT-1186-A04.

When this SAP version 1.0 was finalized and signed, for 384 subjects randomized in Study MT-1186-A02, 202 subjects who have successfully completed Study MT-1186-A02 were enrolled in this MT-1186-A04 study.

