7.2. Type I Error Control

Type I error will not be controlled for multiplicity adjustment between the primary endpoint and the secondary endpoints. All statistical tests for primary endpoint as well as for other endpoints will be done at 2-sided significance level with nominal values of 20% and 5%,

Mitsubishi Tanabe Pharma America, Inc.

respectively. Point estimates of treatment differences will be accompanied with 2-sided 80% and 95% confidence intervals where applicable respectively.

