9.2.1. Primary Endpoint

9.2.1.1. Primary Analysis

The primary efficacy endpoint (TIMETO) is Time from the randomization date in Study MT-1186-A02 to at least a 12-point decrease in ALSFRS-R or death, whichever happens first. All available event data regardless of use of additional/new AMX0035 treatment (ICE1) drug will be included. This endpoint will be summarized using the number of events and percentages and displayed by Kaplan-Meier estimates stratified by treatment group. The comparison between Treatment Group 2 versus Treatment Group 1 will be performed using stratified log rank test with stratifications factors used during MT-1186-A02 randomization:

- ALSFRS-R decline rate (DR) score from the MT-1186-A02 screening period (2 levels strata of -1,-2 or -3,-4)
- Geographical region (GR) 3 levels strata of Europe, America, or Asia Pacific.

This statistical test will be done as 2-sided with a nominal 20% significance level. The SAS code planned for the analysis is outlined below.

The primary efficacy endpoint (TIMETO) will also be analyzed using the Cox Proportional Hazard Model with terms for treatment (TRTP) as explanatory variable and baseline ALSFRS-R score (BASE), and the MT-1186-A02 randomization strata as covariates (DR and

Mitsubishi Tanabe Pharma America, Inc.

GR). This statistical test will be done as 2-sided with a nominal 20% significance level. Point estimates of treatment differences will be accompanied with 2-sided 80% CIs.

The SAS code planned for the analysis is outlined below.

[figure not shown]
Individual Component Analysis

To investigate the effect on the individual component for the primary endpoint,

- Time from the randomization date in Study MT-1186-A02 to at least a 12-point decrease in ALSFRS-R
 - ➤ Change in ALSFRS-R Total Score at time the event occurred
 - > Change in ALSFRS-R Bulbar Function Score at time the event occurred
 - ➤ Change in ALSFRS-R Limb Function Score at time the event occurred
 - > Change in ALSFRS-R Respiratory Function Score at time the event occurred
- Time from the randomization date in Study MT-1186-A02 to death

The above parameters will be descriptively summarized.

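### King's-stage progression proportions are tested without the randomisation strata that the log-rank test of the same events uses; the cost in power depends on how prognostic the strata are

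*SAP*

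**What the plan says.** SAP 9.2.2.2.3 defines two progression events from King's stage: any decline from baseline, and a decline of at least 2 stages. It compares the arms on the proportion with each event by Week 96, and on the time to each event, "using chi square test for proportions, as well as the time to these events using stratified log rank test using the randomization strata". The strata are decline rate and region: "2 levels strata of -1,-2 or -3,-4), Geographical Region (3 levels strata of Europe, America or Asia Pacific". The grammar attaches them to the log-rank test; the chi-square test has none.

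The paragraph ends: "Comparisons will be made between treatment groups on an overall basis", "as well as controlling for King's stage at baseline using Cochran–Mantel–Haenszel test (CMH". So one adjusted proportion test is planned, and its adjustment factor is baseline King's stage.

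Elsewhere the strata are used routinely. SAP 9.2.1.1 tests the primary endpoint by a "stratified log rank test with stratifications factors used during MT-1186-A02 randomization" and puts the same factors in the Cox model. The ALSFRS-R MMRM includes them, and %SVC and body weight inherit that model. Protocol 17.4.5.6 plans only frequencies and shift tables for King's stage, so the SAP is the only source of this test.

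On status, SAP 9.2.2.2 states: "The following exploratory endpoints will be analyzed without overall Type I error correction". SAP 7.2 says tests of the primary and the other endpoints, respectively, "will be done at 2-sided significance level with nominal values of 20% and 5"%, so the King's tests are read at a nominal 5%.

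**The concern.** When allocation is balanced within strata, between-stratum variation cancels out of the treatment difference. A pooled chi-square test still counts that variation in its standard error. If the strata predict the outcome, the standard error is too large, the true type I error falls below 5%, and power is lost.

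Prognostic strata are plausible here. King's stage is derived from ALSFRS-R items, and one stratum factor is the ALSFRS-R decline rate during screening. Baseline King's stage is not a substitute: stages 1 to 3 count the regions involved, not the speed of decline.

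At stake are some sensitivity in an exploratory comparison, and two tests of the same event that handle the randomisation factors differently without a stated reason.

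**Working it through.** **The plan's own figure.** The SAP gives no power, event rate or effect size for the King's proportions. Its only power figure, 70%, concerns the primary endpoint (hazard ratio 0.775, 2-sided alpha 20%, "planned sample size of 190 subjects per group initially randomized in Study MT-1186-A02"; Protocol 17.2 adds 65% event-free at Week 48 in the control group). Assuming exponential times over 96 weeks:

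- Event proportions are 1 - 0.65^2 = 0.5775 and 1 - 0.65^(2 x 0.775) = 0.487.
- Events: 190 x (0.5775 + 0.487) = 202.
- Power: Φ(√(202.28/4) x |ln 0.775| - 1.282) = Φ(1.813 - 1.282) = 70.2%.

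The figure reproduces but does not bear on the King's test.

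**Mechanism.** Let w_k be the share of stratum k, p_k its event risk and p̄ the pooled risk. The pooled test uses p̄(1 - p̄) = Σw_k p_k(1 - p_k) + Σw_k(p_k - p̄)². Under balanced allocation only the first term belongs to the treatment difference. With R = Σw_k p_k(1 - p_k) / [p̄(1 - p̄)], the true type I error is about 2[1 - Φ(1.96/√R)].

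Two examples on decline rate alone, with half the subjects in the fast-decline stratum (all values assumed):

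- Risk 60% (slow) v 75% (fast), odds ratio 2: R = 0.21375/0.219375 = 0.974, and 1.96/√R = 1.986. Type I error 4.7%.
- Risk 40% v 85%, odds ratio 8.5: R = 0.18375/0.234375 = 0.784, and 1.96/√R = 2.214. Type I error 2.7%.

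**Simulation.** 40,000 trials per scenario, about 190 per arm, exact balance within 2 x 3 = 6 strata, 2-sided 5%. Assumptions: fast-decline share 20% or 40%; region shares 45/35/20%; base-cell risk 40%, 60% or 80%; treatment odds ratio 0.55 for power. The tests were:

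- Pearson chi-square without continuity correction: (p̂₁ - p̂₀)² / [p̄(1 - p̄) x 2/n], with n subjects per arm.
- CMH over the 6 strata: [Σ(a_k - m_k/2)]² / ΣV_k, where V_k = n_k² m_k(T_k - m_k) / [T_k²(T_k - 1)]. Here n_k is the number per arm in the stratum, T_k = 2n_k, m_k the events in both arms, and a_k the events in the daily arm.

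| Strata (odds ratio: decline rate, region) | Chi-square type I error | Power gain from CMH, points |
|---|---|---|
| Not prognostic (1, 1) | 4.8-5.3% | -0.2 to 0.1 |
| Weak (2, 1.25) | 4.1-4.9% | 0.3-0.7 |
| Moderate (3, 1.5) | 3.7-4.7% | 0.7-2.7 |
| Strong (5, 2) | 3.2-4.5% | 2.8-8.0 |

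CMH type I error was 4.8-5.3% throughout. A further simulation with 192 per arm (384/2) covered the two examples above, with no or modest region effects. At 60% v 75%, chi-square type I error was 4.5-4.7% and the gain about 0.3-1.8 points. At 40% v 85% these were 2.8-2.9% and about 9-11 points.

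**The case against.** The strongest reply is that this hardly matters. King's stage is exploratory, p-values are nominal, and a conservative test cannot create a false claim. The same events already get a log-rank test stratified by decline rate and region, and the wording on overall and stage-controlled comparisons reads as a deliberate crude-plus-adjusted pair. An unadjusted test beside crude percentages is valid. All of this stands, and it sets the severity. It does not supply a proportion test that respects the randomisation factors.

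Four stronger readings are tempting, and the documents do not support them:

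- **That power is certainly lost.** This needs prognostic strata. The documents give neither event rates nor subject shares by stratum.
- **That the chi-square test is invalid or anti-conservative.** Any error runs the other way.
- **That this is the plan's only unstratified comparison.** The restricted mean survival time analysis in SAP 9.2.2.1.3.1 names no strata (its code is not visible). Nor does the Gehan-Wilcoxon sensitivity test for CAFS in Protocol 17.4.5.4.
- **That stratifying would reconcile the proportion and log-rank results.** They can still differ. The log-rank test uses event timing and censors dropouts at their first missing assessment, while the stage derivation carries the last stage forward.

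Incomplete follow-up may well matter more for this test. The proportion runs to Week 96, but SAP 4.2 reports that 202 of 384 randomised subjects entered MT-1186-A04, and both studies were stopped. That is a separate problem, which stratification does not touch.

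**Conclusion.** The point holds as a minor one. No planned test of the King's progression proportions uses the randomisation strata, although the log-rank test of the same events does.

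If the strata are prognostic, the chi-square test is conservative, with type I error of about 2.7-4.9% at a nominal 5% over the assumed rates. The power loss is nil to about 3 points for weak or moderate strata, and about 3-8 points or slightly more for strong strata. If they are not prognostic, there is no loss. These sizes rest on assumed stratum shares, risks, odds ratios and exact balance within strata; only the missing strata are fixed by the text.

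The change is worth making because it is close to free. CMH held its level in every scenario and cost at most 0.2 points of power when the strata carried no information.

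**What to change.** In SAP 9.2.2.2.3, replace the chi-square test with a CMH test stratified by decline rate x region (6 strata), and report a stratum-weighted risk difference with 95% CI. Keep the CMH test by baseline King's stage as an additional analysis. If the crude chi-square test is retained as the main comparison, say why it omits the strata.

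The cost is one line of SAP wording and one table statement, with no new data. With 384/6 = 64 subjects per stratum on average, sparse strata are unlikely to be a general problem, though actual stratum sizes are not given. SAP 5.2 says the final analysis will not be conducted, so the change applies to the interim analysis. Incomplete follow-up to Week 96 needs its own treatment.
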